2.2. Outcome Measures

2.2.1. *Primary Outcome*

Primary outcome measures: Recorded measurements of BP as compared to the ICU standard of care monitoring, including both arterial line measurements and cuff-based measurements of the arm.

2.2.2. *Secondary Outcomes*

Secondary outcome measures: Recorded measurements of other physiologic signals such as HR, pain, temperature, cerebral blood flow, aEEG-like waveforms, and respiratory rate as compared to ICU standard of care monitoring. Accelerometry will be captured using these devices, and in a subset of study participants, will be compared to video recordings to validate the accuracy of these devices for detecting body position and movement (as these are known to affect BP measurement). Devices may also evaluate subjects' respiratory equipment. Questionnaire data examining parent opinions on use of wearable sensors compared to standard of care devices.

3. Study Design

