3.1. Target Population

Two distinct populations will be targeted for participation in this study. The first includes patients admitted to intensive care units (ICUs) including the pediatric intensive care unit (PICU), the neonatal intensive care unit (NICU), and the cardiac intensive care unit (CCU). This includes all ICUs at the Ann & Robert H. Lurie Children's Hospital of Chicago (Lurie Children's) and the NICU at Prentice Women's Hospital (Prentice). The first target population will contribute primarily to the collection and validation of physiologic signals including BP, HR, pain, temperature, cerebral blood flow, aEEG-like waveforms, and respiratory rate. The second target population includes any neonate, infant, or child whose parent or guardian consents to a one time visit to the Center for Autonomic Medicine in Pediatrics (CAMP) at Lurie Children's. The second population will be more physically active than the ICU population and contribute primarily to the capture and validation of these same physiologic signals in the context of increased motion, which is known to produce artifact in such recordings. The wearable sensors must be tested in a range of patients across age groups in order to validate the signals and data recorded by the devices. This requires the inclusion of patients of various ages, including neonates, infants, and children.

Up to 500 patients will be enrolled at Lurie Children's and Prentice.

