Cuff-based blood pressure: While the wearable sensors are attached to participants in both the ICU and non-ICU populations, the participants will also be monitored with the normal standard of care monitoring montage. In addition, during one 3- or 4-hour period while the wearable sensors are attached to the patient, a member of the study team may take the participant’s BP using the ICU standard cuff-based method every 15 minutes. Cuff-based measures typically happen every 15-60 minutes for standard clinical care, depending on the stability of the patient and physician discretion. In the ICU population, if a standard clinical cuff-based BP measure is taken during the 15-minute time epoch, the clinical measurements will be used rather than obtaining a separate research measurement. Outside of this 3- or 4-hour window and for the remainder of the study duration in the ICU cohort, cuff-based BP measures will be made only as frequently as needed for standard clinical care.

Skin temperature: While the wearable sensors are attached to the participant, skin temperatures will be taken using a standard infrared thermometer. These measurements will be made at the same interval as the above cuff-based BP, over the same 4-hour period by a member of the study team. Outside of this 4-hour window, no skin temperature measures will be made for research purposes.

Device data: Wearable sensors can stream data continuously using near field communication (NFC) or Bluetooth technology. An encrypted laptop, iPad, or similar device will be left in the patient room and used to capture the continuous data stream from the wearable sensor. Additionally, wearable sensors can include onboard memory, and physiologic streams may be recorded to this onboard memory until transfer to an encrypted laptop for analysis.

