5.2. Statistical Plan

Measurements made through clinical standard of care will be compared to the measurements recorded by the wearable sensors. Distribution checks for normality and data accuracy will be completed for each individual and for the entire study prior to all analyses. For continuous measures of physiology, 30 second epochs will be defined for each method for comparison. For non-continuous CB-BP measures, each measure will be matched and compared to the 30-second epoch during which the measure was captured. We will further check for time lags in the relationships between methods by applying peak-picking methods to lagged regression plots for all pairs of measures.

Agreement and correlation of wearable sensor measures to standard of care measures will be assessed in two ways. First, Bland-Altman plots will be created to assess agreement between each measurement system via bias and precision, which reflect the mean or average difference between two methods and the variation in these differences, respectively. Our second method consists of individual correlations between methods assessed for each person. This correlational method will supplement additional methods, and can be directly transformed to variance shared between wearable sensor and standard of care measures, a common metric of reliability of any measure.

Formal tests of bias, precision, and correlations: While the above methods will yield useful statistics, they need to be extended to deal with the structured nature of our data. Specifically, our data are clustered, meaning that we have multiple observations within each person and multiple people in our sample, which violates standard independence assumptions inherent to many models. We propose to estimate bias and correlation/reliability using multi-level models, which yield the same statistics discussed above but account for the fact that observations taken from the same patient are more related than comparisons involving different patients.

Statistical power: The large amount of within-person data provides incredibly high statistical power for all planned and many secondary data analyses, allowing this data set to answer all proposed questions. Previous work on power in multilevel models found greater than 99% power to detect associations with the planned observations suggested here within comparable nested designs.

6. References

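### Does section 5.2 leave precision out of the cluster-aware analysis, so that its uncertainty would be understated?

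*Protocol*

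**What the plan says.** The primary outcome in section 2.2.1 is "Recorded measurements of BP as compared to the ICU standard of care monitoring", from both arterial lines and arm cuffs. Section 5.2 assesses agreement first with Bland-Altman plots, "via bias and precision, which reflect the mean or average difference between two methods and the variation in these differences". Precision is therefore defined as the spread of the paired differences.

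The next paragraph of 5.2 is headed "Formal tests of bias, precision, and correlations". It says that the simple methods need extending because repeated observations sit within patients, "which violates standard independence assumptions inherent to many models". The remedy follows: "We propose to estimate bias and correlation/reliability using multi-level models, which yield the same statistics discussed above". The rest of that sentence says that these models allow for the closer relation of observations from the same patient.

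On the amount of data: for continuous signals, "30 second epochs will be defined for each method for comparison". Section 3.6 allows, in one 3- or 4-hour window, "BP using the ICU standard cuff-based method every 15 minutes". Section 3.1 states: "Up to 500 patients will be enrolled".

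**The concern.** The heading promises formal work on three quantities, but the sentence that assigns the multi-level model names two. Read literally, bias and correlation get a cluster-aware analysis and precision stays with the plain Bland-Altman calculation.

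That would matter because precision shows how far a single sensor reading may be off. A sensor can have no average bias and still be unusable reading by reading. If every pair counted as independent, thousands of 30-second epochs from a few patients would give a very tight interval around the limits of agreement. Enrolling more patients would not remove the overstatement, because the correct and the pooled standard errors shrink together.

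**Working it through.** **The protocol's own figure.** The only figure for statistical performance in section 5.2 is power above 99% to detect associations. It cannot be reproduced, because no effect size, alpha, SD or intraclass correlation (ICC) is given. It does not concern precision.

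**Side-by-side reading.** Section 5.2 introduces three statistics: bias, precision and correlation. The next paragraph names the same three in its heading and gives clustering as the reason for going further. It then says that the models return the statistics already discussed while allowing for clustering. A multi-level model of paired differences yields a mean (bias) and between- and within-patient variances, whose sum is the spread of the differences. The model therefore delivers precision as the section defines it.

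**What a pooled analysis would do if someone ran one.**

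Inputs from the protocol:
- cuff pairs per patient: m = 4 h × 4 per hour = 16;
- epochs in the same 4 hours: m = 4 × 120 = 480;
- number of patients K: up to 500.

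Assumed, because the protocol does not give them: K = 50 as a smaller case; ICC of the differences b = 0.05, 0.2 or 0.5; normal, balanced data; equal variance in all patients; no serial correlation within a patient. Total variance is set to 1, w = 1 − b and N = K × m.

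*Point estimate.* The expected pooled variance is w + b(N − m)/(N − 1). For K = 50, m = 16, b = 0.5 it is 0.5 + 0.5 × 784/799 = 0.9906, with square root 0.995. In simulation the mean pooled SD was 0.9993 / 0.9976 / 0.9938 of the true SD with 16 pairs, and 0.9995 / 0.9979 / 0.9935 with 480. The limits of agreement are thus within 1%.

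*Uncertainty of a 95% limit.*
- Pooled: SE = √(1/N + 1.96²/(2N)).
- Clustered: SE = √((b + w/m)/K + 1.96² × V/4), with V = 2(b + w/m)²/(K − 1) + 2w²(1 − 1/m)²/(K(m − 1)).

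Example with K = 50, m = 16, b = 0.2:
- pooled √(0.00125 + 0.002401) = 0.0604;
- V = 0.002551 + 0.001500 = 0.004051;
- clustered √(0.005 + 0.003891) = 0.0943;
- ratio 0.0943/0.0604 = 1.56.

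| K | m | ICC 0.05 | ICC 0.2 | ICC 0.5 |
|---|---|---|---|---|
| 50 | 16 | 1.13 | 1.56 | 2.47 |
| 50 | 480 | 3.16 | 6.83 | 12.78 |
| 500 | 16 | 1.13 | 1.56 | 2.46 |
| 500 | 480 | 3.16 | 6.81 | 12.72 |

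With an assumed SD of 8 mmHg and 50 patients, the half-width with cuff pairs is 1.96 × 8 × 0.0604 = 0.95 mmHg pooled, against 1.07 to 2.34 mmHg correct. With 480 epochs it is 0.17 against 0.55 to 2.21 mmHg.

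*A test of the SD against a threshold.* The protocol has no such test. If one were built on pooled pairs at one-sided 5%, with the true SD exactly at the threshold and 50 patients, its simulated error would be 5.5 / 10.6 / 26.5% (16 pairs) and 14.8 / 41.5 / 50.8% (480). With the true SD 10% above the threshold, false passes would be at most 0.7% and 2.5%.

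**How far the epoch rows apply to blood pressure.** The protocol's background says that arterial lines are used only in the most critically ill patients, and that the rest of the ICU population has periodic cuff readings. Continuous reference pressure therefore exists only in a subset. For most participants the cuff rows are the relevant ones. Within the arterial-line subset, recordings longer than 4 hours would raise the factor further.

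**The case for a change.** The best case for a change is that the protocol itself states the problem, names three quantities and assigns the remedy to two, so this is more than detail left for later. Even on the generous reading, a multi-level model gives two variance components and the sentence does not say which one is precision. Reporting only the residual SD would understate the spread by √(1 − ICC): 0.95 / 0.84 / 0.71 at ICC 0.1 / 0.3 / 0.5. That would be an error in the estimate itself. The cure is one added phrase.

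The wording mismatch stands. The rest is weaker. Section 5.2 defines precision as the variation in the differences between methods. The residual component alone is not that quantity once patients differ in their mean difference, so the definition already points to the total. Nothing commits an analyst to pooling, and the paragraph gives the reason against it.

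One caveat runs the other way. The near-correct pooled limits depend on similar variance across patients. Suppose half the patients were ICU patients with 8,640 epochs (72 h × 120) and half were non-ICU children with 360 (3 h × 120), a 24:1 weighting. If the non-ICU SD were 1.5 times as large, the pooled SD would be √((24 + 2.25)/25) = 1.025 against a patient-equal √((1 + 2.25)/2) = 1.275, about 20% lower. At twice the SD it would be about 33% lower. These ratios are assumptions. They bear mainly on signals recorded continuously in both groups, not on cuff pressure. Adding the word precision to the sentence would not settle that question either.

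**Conclusion.** No change follows. The sentence is elliptical: precision stands in the paragraph's heading, in its reasoning and among the statistics that the models are said to return, but not in the short list. A statistician following the paragraph as a whole would take precision from the same model of paired differences.

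The interval factors (1.13 to 2.47 for cuff pairs, 3.2 to 12.8 for 480 epochs) and the test errors (5.5 to 51%) are correct under the assumed ICCs. They describe a pooled interval and a threshold test that the protocol does not contain. The pooled limits themselves would be within 1% with 50 patients and closer with 500, provided that variances are similar across patients and across the ICU and non-ICU groups. The variance components to be summed and the form of the interval belong in the statistical analysis plan, which is not at hand. Their absence from the protocol is not a fault.

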3.6. Study Procedures

Device application: In both the ICU and non-ICU study populations, standard-of-care devices will be used in all subjects and this data will be compared to that collected using novel wearable sensors suggested in this study. After participants are consented, multiple wearable sensors (up to 5) will be placed on the participant for the duration of the study. Multiple devices are required to estimate BP. One or more devices will be placed on the chest or back, and one or more additional devices will be placed peripherally (e.g. leg, foot, arm, hand, head, or ear). One or more additional devices may be placed on the patient's respiratory support device if applicable. Placing multiple devices will allow determination of which location provides the best signals in specific populations. These devices will be placed using a medical grade skin adhesive similar to the ones used in the ICUs, which will minimize the

risk of skin irritation or allergic reaction. Alternatively, we are currently testing a “soft wrap-around device” (similar to that currently used for blood pressure monitoring in the premature babies) with a sensor. The soft wrap-around device is composed of hypoallergenic cotton. Overlying this cotton, and not touching the subject’s skin, may include Coban wraps, paper tape, or a Velcro adhesion mechanism. Given the very small size of premature infant in the NICU, we may incorporate this new technology as needed in the NICU. In the ICU population, devices will be left in place for up to 72 hours, but will either be checked by the study or clinical team to ensure skin integrity and signal quality at least once every 24 hours. In the non-ICU population, devices will be left in place for up to 3 hours during a study visit to CAMP.

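### The agreement analysis describes no bias or limits of agreement by setting, although CAMP children are enrolled as a distinct population to test the sensors under motion

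*Protocol*

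**What the plan says.** Protocol section 3.1 states: "Two distinct populations will be targeted for participation in this study". The ICU patients serve mainly to collect and validate the signals. The CAMP children are expected to be more active and serve mainly for "validation of these same physiologic signals in the context of increased motion, which is known to produce artifact in such recordings". The same section says that the sensors "must be tested in a range of patients across age groups in order to validate the signals and data recorded by the devices". Up to 500 patients are to be enrolled, with no split by setting or age.

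Section 5.2 sets out Bland-Altman bias and precision, a correlation for each person, and multi-level models. The data structure it names is "multiple observations within each person and multiple people in our sample", and the models are there to "account for the fact that observations taken from the same patient are more related than comparisons involving different patients". Distribution checks are planned per individual and for the study as a whole. Setting does not appear as a term, stratum or subgroup.

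The settings also differ in recording time. In the ICU, "devices will be left in place for up to 72 hours"; at CAMP the maximum is 3 hours (section 3.6).

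**The concern.** Section 3.1 gives a scientific reason to expect the sensor to behave differently at CAMP: motion produces artifact. Section 5.2 treats all participants as one sample of persons. A random effect for person handles the correlation of repeated readings, but it does not separate the two settings.

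Nothing else in the plan fills the gap. A per-person correlation does not show bias or limits of agreement. The accelerometry and video comparison in section 2.2.2 validates detection of position and movement, not agreement of blood pressure by setting.

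At stake is the question for which CAMP is enrolled. If error is larger there, the overall limits understate it. If the bias differs, the reported bias is an average that describes neither setting.

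**Working it through.** **The plan's own figure.** Section 5.2 quotes power above 99% from previous work, without alpha, effect size, SD or number of persons. It cannot be reproduced, and this point does not depend on it.

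**Inputs from the protocol.** Cuff readings may be taken every 15 minutes in one 3- or 4-hour window, and clinical cuffs typically occur every 15 to 60 minutes (section 3.6).
- CAMP: 3 h × 4 per hour = 12 pairs per child, a maximum.
- ICU: 12 pairs if only a 3-hour window is used, or 72 h × 1 to 4 per hour = 72 to 288 pairs, upper bounds at full wear.

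**Assumptions (the protocol gives none).** Error SD is 6 mmHg in the ICU and 10 at CAMP, with equal bias and half of each variance between persons. The between- and within-person variances are then each 18 in the ICU and 50 at CAMP. CAMP/ICU splits are 250/250, 100/400 and 50/450.

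**Formulas.** In a random-intercept model with common variances and large samples:
- between = average of the group values, weighted by persons
- within = average of the group values, weighted by observations
- overall SD = √(between + within)
- CAMP coverage with equal bias = 2Φ(1.96 × overall SD / 10) − 1

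**Equal cuff counts, 250/250, 12 pairs each.** Between = within = 0.5 × 18 + 0.5 × 50 = 34. SD = √68 = 8.25. CAMP coverage = 2Φ(1.616) − 1 = 89%. ICU coverage = 2Φ(1.96 × 8.25 / 6) − 1 = 99%.

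**Unequal counts, 100/400, 72 ICU cuffs.** Between = 0.8 × 18 + 0.2 × 50 = 24.4. CAMP supplies 1,200 of 30,000 observations (4%), so within = 0.96 × 18 + 0.04 × 50 = 19.28. SD = √43.68 = 6.61. CAMP coverage = 80%.

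| CAMP/ICU | ICU cuffs per child | CAMP differences inside overall 95% limits |
|---|---|---|
| 250/250 | 12 / 72 / 288 | 89% / 86% / 85% |
| 100/400 | 12 / 72 | 83% / 80% |
| 50/450 | 12 / 72 | 80% / 78% |

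REML fits to simulated trials agree with these values to within about one percentage point. The shortfall is present with equal cuff counts, so it does not depend on the longer ICU recordings.

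**Sensitivity.** With a CAMP SD of 8, coverage is 92% (250/250, 12 each) to 87% (50/450, 72 ICU cuffs). With SD 12, the same two cases give 88% and 71%. With SD 6 in both settings and equal bias, it is 95% in every case. If CAMP error were smaller, say SD 4, the direction reverses: at 250/250 with 12 each, between = within = 0.5 × 18 + 0.5 × 8 = 13, SD = √26 = 5.10, and CAMP coverage is 99%.

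**Different bias, equal SD 6.** Take a true bias of 0 in the ICU and 5 mmHg at CAMP. The reported bias is about 2.4 to 2.5 (250/250), 1.0 (100/400) or 0.5 (50/450). At 250/250 with 12 each, the group difference adds 0.25 × 25 = 6.25 to the between-person variance. SD = √(24.25 + 18) = 6.5, and the limits are 2.5 ± 12.74. CAMP coverage is Φ((15.24 − 5)/6) − Φ((−10.24 − 5)/6) = 95%. Here the limits still hold and the reported bias is what misleads.

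**The case against.** The strongest objection is that this is an absence, not an error. Covariates, strata and variance structures often sit in an analysis plan, and one may exist. Section 5.2 gives no model formula, and setting, being a between-person factor, can be added without changing the rest. This stands in part. A reader might infer that the protocol declares pooling, or that section 3.1 promises separate estimates; it does neither. What remains is that section 5.2 does describe the structure of the agreement model, and that structure does not serve the purpose given for enrolling CAMP.

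Other stronger readings also lack support:

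- **All of the primary outcome is blended.** Section 2.2.1 names arterial-line and cuff comparators. The protocol's background says arterial lines are used only in the most critically ill, so children on a one-time CAMP visit would not be expected to have one.
- **CAMP always looks better than it is.** That holds only if CAMP error is larger or its bias differs enough, and the cases above show exceptions.
- **Long ICU recordings swamp CAMP.** Maximum 30-second epochs per child are 8,640 against 360, a ratio of 24 to 1. That weighting applies to a plot pooled over epochs. The multi-level model weights bias nearly by person.
- **Age groups are distorted in the same way.** Section 3.1 requires a range of ages, and eligibility allows it. No age difference in error has been shown here.
- **The models leave out precision.** The sentence "We propose to estimate bias and correlation/reliability using multi-level models, which yield the same statistics discussed above" lists only bias and correlation, but its reference back to the earlier statistics, under the heading "Formal tests of bias, precision, and correlations", most naturally includes precision. This is not an error.

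It is also fair to say that setting is a proxy for motion, and that the accelerometry could be used to model motion directly. That would be a useful addition. Setting is the simpler step and matches how section 3.1 defines the populations.

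**Conclusion.** The point holds for measures taken in both settings: as described, the analysis yields one blended bias and precision and cannot answer the motion question. Under the main assumptions (SD 6 and 10 mmHg, half the variance between persons), the overall 95% limits contain about 78% to 89% of CAMP cuff differences, depending on the split and the cuff counts. Every SD, variance share, bias and split is assumed, and the cuff counts are maxima. Equal error and bias would mean no distortion, but only estimates by setting can show that. The protocol states no acceptance limit, so no pass/fail decision turns on the blended figure. The weight is minor to moderate, with medium confidence.

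**What to change.** In section 5.2, for measures taken in both settings, add setting (ICU or CAMP) as a term in the multi-level model of paired differences, and let the between- and within-person variances differ by setting. Report bias and 95% limits of agreement for ICU and CAMP separately, with patient-level confidence intervals (for example, a bootstrap that resamples patients). Keep the overall figure as a summary. Report estimates for neonates, infants and children as descriptive only.

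The cost is wording and modest extra analysis; no new data are needed. Intervals are wider for the smaller group. With 12 pairs per CAMP child and half the variance between persons, the 95% interval half-width of a limit is about 3.0, 2.1 or 1.3 mmHg at SD 10 with 50, 100 or 250 children (1.8, 1.3 or 0.8 at SD 6). Splitting CAMP into three equal age groups (about 17, 33 or 83 children each) widens this to about 5.1, 3.7 or 2.3 mmHg at SD 10, which is why age-group limits should stay descriptive.
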